1.1 Primary Objective

Specific Aim 1: Determine if PFD is associated with fewer surgical complications and less harm to patients than PFDD.

Hypothesis: PFD will be associated with fewer surgical complications and less potential harm to patients than PFDD.

Anticipated Outcome: Cerebrospinal fluid (CSF)-related complications ≤ 6 months (e.g. CSF leak, pseudomeningocele, aseptic meningitis, infection, hydrocephalus), and the requirement for additional surgery for wound revision or CSF diversion will be lower after PFD compared with PFDD.

Corresponding Variable Names for 'Complications':

- **CSF leak:** Form 16634 (10), ChiariPOCSFLeak
- **Pseudomeningocele:** Form 16402 (4), ChiariPOPseudomen
- Aseptic meningitis: Form 16420 (5), ChiariPOchemicalMeningitis
- True meningitis: Form 16416 (5), ChiariPOTrueMeningitis
- Infection: Form 16416 (5), ChiariPOWRInfection
- Hydrocephalus: Form 16427 (6), Hydrocephalus
- Cervical Instability: Form 16431 (6), CervicalInstability

Corresponding Variable Names for 'Additional Surgery for Wound Revision or CSF Diversion'

- Required External drainage of CSF: Form 16404 (4), ChiariPOExtDrainageCSF
- Simple Over-Sewing of Wound for CSF Leak: Form 16413 (5), SimpleOSWoundCSF
- Surgical revision of wound in operating room: Form 16414 (5), ChiariPOSurgRevision
- Chemical Meningitis: Form 16420 (5), ChiariPOchemicalMeningitis
- CSF Leak: Form 16415 (5), ChiariPOWRCSFLeak
- Infection: Form 16416 (5), ChiariPOWRInfection
- **Pseudomeningocele:** Form 16419 (5), ChiariPOWRPseudomen

Outcome –Count, Number of patients with a complication

Timeframe - ≤ 6 months

Time Period	Complication			
Intra-Op				
	Vascular Injury			
	Hemorrhage Requiring Evacuation			
	Neurological Injury			
	Death			
	Other Complications			
< 6 Months				
	Pseudomeningocele			
	CSF Leak			
	External Drainage Required			
	Simple Over-Sewing of Wound for CSF Leak			
	Surgical Revision of Wound in OR			
	Chemical Meningitis			
	True Meningitis			
	Hydrocephalus			
	Cervical Instability			
	Other Complications, Procedure Specific			
	Other Complications, Not Procedure			
	Specific			
> 6 Months				
	Cervical Instability			
	Infection			
	Hydrocephalus			
	Other Complications, Procedure Specific			

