# • Complications ≤ 6 months after PFD or PFDD

- Pseudomeningocele: an extradural and/or subcutaneous fluid collection resulting in discomfort or pain, limitation of movement, or CSF leak. Radiological evidence of fluid collection alone is not sufficient for diagnosis of pseudomeningocele.
- CSF Leak
- Hydrocephalus: requires external drainage, shunting, or endoscopic 3rd ventriculostomy.
- Infection: clinical diagnosis that may include fever, wound drainage, dehiscence, or elevated laboratory parameters in association with antibiotic treatment ± surgical debridement.
- Chemical (or aseptic) meningitis: clinical diagnosis prompting medical treatment (e.g. steroids); lumbar puncture and analysis of CSF cell profile not required but will be tracked if available.
- True meningitis: lumbar puncture and positive cultures required.
- Cervical instability
- Cerebellar ptosis with intractable headaches
- Need for interventions for complication management <6 months after initial PFDD or PFD
  - External drainage for the following:
    - > Hydrocephalus
    - ➢ CSF leak
    - > Pseudomeningocele
    - ➢ Infection
    - Shunt malfunction/infection
  - Simple over-sewing of wound for CSF leak
  - Surgical revision in operating room for the following:
    - ➢ CSF leak
    - ➢ Infection
    - Pseudomeningocele
  - Lumbar puncture and steroids for the following:
    - Chemical meningitis
    - > True meningitis
  - Implantation of ventriculo-peritoneal or other permanent shunt or endoscopic 3rd ventriculostomy for hydrocephalus.
  - Cervical collar and/or fusion for cervical instability
  - Cerebellopexy for cerebellar ptosis
- Complication  $\leq 12$  (+/- 2 months) months after initial PFDD or PFD
  - Pseudomeningocele: an extradural and/or subcutaneous fluid collection resulting in discomfort or pain, limitation of movement, or CSF leak. Radiological evidence of fluid collection alone is not sufficient for diagnosis of pseudomeningocele.

- CSF leak
- Hydrocephalus: requires external drainage, shunting, or endoscopic 3rd ventriculostomy.
- Infection: clinical diagnosis that may include fever, wound drainage, dehiscence, or elevated laboratory parameters in association with antibiotic treatment ± surgical debridement.
- Chemical (or aseptic) meningitis: clinical diagnosis prompting medical treatment (e.g. steroids); lumbar puncture and analysis of CSF cell profile not required but will be tracked if available.

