#### $\circ$ Complication $\leq 12$ (+/- 2 months) months after initial PFDD or PFD

- Pseudomeningocele: extradural and/or subcutaneous fluid collection resulting in discomfort or pain, limitation of movement, or CSF leak. Radiological evidence of fluid collection alone is not sufficient for diagnosis of pseudomeningocele.
- CSF leak
- Hydrocephalus: requires external drainage, shunting, or endoscopic 3rd ventriculostomy
- Infection: clinical diagnosis that may include fever, wound drainage, dehiscence, or elevated laboratory parameters in association with antibiotic treatment ± surgical debridement.
- Chemical (or aseptic) meningitis: clinical diagnosis prompting medical treatment (e.g. steroids); lumbar puncture and analysis of CSF cell profile not required but will be tracked if available.
- Cervical instability
- Cerebellar ptosis with intractable headaches
- Need for surgical procedures for complication management ≤12 (+/- 2 months) months after initial PFDD or PFD
  - External drainage for the following:
    - ➢ Hydrocephalus
    - $\succ$  CSF leak
    - Pseudomeningocele
    - > Infection
    - Shunt malfunction/infection
  - Simple over-sewing of wound for CSF leak
  - Surgical revision in operating room for the following:
    - $\succ$  CSF leak
    - ➢ Infection
    - > Pseudomeningocele
  - Lumbar puncture and steroids for the following:
    - Chemical meningitis
    - > True meningitis
  - Implantation of ventriculo-peritoneal or other permanent shunt or endoscopic 3rd ventriculostomy for hydrocephalus.
  - Cervical collar and/or fusion for cervical instability
  - Cerebellopexy for cerebellar ptosis

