5.2 Adverse Events and Serious Adverse Events

SAFETY ASSESSMENTS

Complications will be recorded at the following time points:

- Intra-operatively
- $\circ \leq 6$ months after initial PFD or PFDD
- 6-12±2 months after initial PFD or PFDD

The following definitions are provided for clarification:

- Pseudomeningocele: an extradural and/or subcutaneous fluid collection resulting in discomfort or pain, limitation of movement, or CSF leak. Radiological evidence of fluid collection alone is not sufficient for diagnosis of pseudomeningocele.
- Hydrocephalus: requires external drainage, shunting, or endoscopic 3rd ventriculostomy.
- Infection: clinical diagnosis that may include fever, wound drainage, dehiscence, or elevated laboratory parameters in association with antibiotic treatment ± surgical debridement.
- Chemical (or aseptic) meningitis: clinical diagnosis prompting medical treatment (e.g. steroids); lumbar puncture and analysis of CSF cell profile not required but

will be tracked if available.

• True meningitis: lumbar puncture and positive cultures required.

Known potential complications include the following:

- Intra-operatively
 - Vascular injury
 - Hemorrhage requiring evacuation
 - Neurologic Injury
 - Cranial nerve injury or palsy
 - Weakness
 - Sensory Changes
 - Bowel Dysfunction
 - Bladder Dysfunction
 - Death
- Complications \leq 6 months or 6-12 \pm 2 months after PFD or PFDD
 - Pseudomeningocele: Form 16402 (4), ChiariPOPseudomen
 - CSF leak: Form 16634 (10), ChiariPOCSFLeak
 - Hydrocephalus: Form 16427 (6), Hydrocephalus
 - Infection: Form 16416 (5), ChiariPOWRInfection
 - Aseptic meningitis: Form 16420 (5), ChiariPOchemicalMeningitis
 - True meningitis: Form 16416 (5), ChiariPOTrueMeningitis
 - Cervical Instability: Form 16431 (6), CervicalInstability

Possible interventions for known complications are as follows:

- Intra-operative complications
 - Evacuation of hemorrhage
 - Open or endovascular repair vascular injury
- $\circ \leq 6$ month or 6-12 ± 2 month postoperative complications
 - Hydrocephalus
 - External ventricular or lumbar drain placement
 - Implantation of ventriculo-peritoneal or other permanent shunt
 - Endoscopic 3rd ventriculostomy for hydrocephalus
 - CSF leak:
 - Over-sewing of wound
 - External ventricular or lumbar drain placement
 - Surgical revision in the operating room
 - Pseudomeningocele
 - Percutaneous drainage
 - External ventricular or lumbar drain placement
 - Surgical revision in the operating room

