7.5.1 Metrics

Primary Outcome: measured as a binary (yes/no) variable. The presence of any of the following items will be considered as a poor outcome (harm to patients):

• Intra-operative Complication

- Vascular injury resulting in dissection or stroke
- Intracranial hemorrhage requiring return to surgery for evacuation
- Neurological injury (new cranial nerve deficit, weakness, sensory loss, bowel or bladder dysfunction)
- Death

• Complication ≤ 12 (+/- 2 months) months after initial PFDD or PFD

- Pseudomeningocele: extradural and/or subcutaneous fluid collection resulting in discomfort or pain, limitation of movement, or CSF leak. Radiological evidence of fluid collection alone is not sufficient for diagnosis of pseudomeningocele.
- CSF leak
- Hydrocephalus: requires external drainage, shunting, or endoscopic 3rd ventriculostomy
- Infection: clinical diagnosis that may include fever, wound drainage, dehiscence, or elevated laboratory parameters in association with antibiotic treatment ± surgical debridement.
- Chemical (or aseptic) meningitis: clinical diagnosis prompting medical treatment (e.g. steroids); lumbar puncture and analysis of CSF cell profile not required but will be tracked if available.
- Cervical instability
- Need for surgical procedures for complication management ≤12 (+/- 2 months) months after initial PFDD or PFD
 - External drainage for the following:
 - > Hydrocephalus
 - ➢ CSF leak
 - Pseudomeningocele
 - ➢ Infection
 - Shunt malfunction/infection
 - Simple over-sewing of wound for CSF leak
 - Surgical revision in operating room for the following:
 - ➢ CSF leak
 - ➢ Infection
 - > Pseudomeningocele
 - Lumbar puncture and steroids for the following:
 - Chemical meningitis
 - True meningitis
 - Implantation of ventriculo-peritoneal or other permanent shunt or endoscopic 3rd ventriculostomy for hydrocephalus.
 - Cervical collar and/or fusion for cervical instability

Secondary Outcomes:

- Treatment Efficacy, measured ≤6 weeks, 3-6 months, and 12 (+/- 2 months) months after surgery:
 - Status of clinical symptoms
 - Status of neurological findings
 - Syrinx diameter (in mm)
 - Spinal alignment (coronal and sagittal Cobb angles)
 - Need for revision of PFDD or PFD
- Quality of life, measured ≤6 weeks, 3-6 months, and 12 (+/- 2 months) months after surgery:

- Chiari Health Index in Pediatrics (CHIP)
- HUI-3.

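### The SAP's primary harm composite matches neither the protocol's composite nor the SAP's own variable list, so some defined harms may go uncounted

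*SAP*

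**What the plan says.** The primary outcome is binary: any listed item makes the patient a harm. The lists are in Protocol 10.3.3 and SAP 7.5.1, and SAP 1.1 maps items to database fields.

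- **Cerebellar ptosis.** The protocol's composite includes "Cerebellar ptosis with intractable headaches" and, among procedures, cerebellopexy. SAP 7.5.1 has neither.
- **Infection.** SAP 7.5.1 defines it as a clinical diagnosis "in association with antibiotic treatment ± surgical debridement", so surgery is not required. SAP 1.1 codes it as "Infection: Form 16416 (5), ChiariPOWRInfection". The same field appears again in SAP 1.1 under "Corresponding Variable Names for 'Additional Surgery for Wound Revision or CSF Diversion", beside entries such as "CSF Leak: Form 16415 (5), ChiariPOWRCSFLeak".
- **True meningitis.** Protocol 7.1 counts it as a harm: "True meningitis: lumbar puncture and positive cultures required". SAP 1.1 gives it a field, and SAP 5.2 lists bacterial meningitis as a harm in both post-operative windows. In the two composites it is named only as an indication for lumbar puncture and steroids.
- **Major injury and death.** Death, vascular injury with dissection or stroke, new neurological deficit, and "Intracranial hemorrhage requiring return to surgery for evacuation" all stand under an intra-operative heading. None has a post-operative counterpart in the composite.

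**The concern.** The trial's main question is whether PFD causes less harm than PFDD. Two programmers, one working from SAP 7.5.1 and one from SAP 1.1, would build different endpoints, and neither would reproduce the protocol's. The events affected are ones that the plan itself calls harm. Few events are expected, especially after PFD, so a handful of patients classified differently would change the reported rates visibly. The SAP footer says that the SAP is based on Protocol Version 6, and it gives no reason for departing from that protocol's composite.

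**Working it through.** **Lists side by side**

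| Harm | Protocol 10.3.3 | SAP 7.5.1 | SAP 1.1 field or row | Elsewhere |
|---|---|---|---|---|
| Infection, antibiotics only | meets definition | meets definition | ChiariPOWRInfection only; no row in the under-6-months block, a row after 6 months | same definition in SAP 5.2 |
| True meningitis | indication only | indication only | ChiariPOTrueMeningitis, and a row under 6 months | harm in Protocol 7.1 and SAP 5.2 |
| Cerebellar ptosis | listed | absent | none | harm to 6 months in SAP 5.2 |
| Cerebellopexy | listed | absent | none | listed in both windows in SAP 5.2 |
| Death, stroke or dissection, neurological deficit | intra-operative heading only | same | intra-operative rows, no field named | the SAE list has death and neurological injury with no timing limit |
| Haemorrhage needing evacuation | intra-operative heading, worded as a return to surgery | same | intra-operative row, no field named | – |

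**Is ChiariPOWRInfection a wound-revision flag?** This is an inference from three facts in SAP 1.1.

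1. CSF leak and pseudomeningocele each have a plain field (ChiariPOCSFLeak, ChiariPOPseudomen) and a WR field (ChiariPOWRCSFLeak, ChiariPOWRPseudomen). Infection has only the WR field.
2. The form numbers run 16414 (surgical revision of the wound), 16415 (WR CSF leak), 16416 (WR infection) and 16419 (WR pseudomeningocele). Infection therefore falls inside the wound-revision block.
3. Form 16416 is also cited for true meningitis. It is the only number in that list attached to two different field names, so at least one entry needs checking.

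**True meningitis.** SAP 7.5.1 reaches it through lumbar puncture and steroids. SAP 5.2 lists lumbar puncture and IV antibiotics against bacterial meningitis. The two passages must be reconciled before that route can be relied on.

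**The plan's own figure.** Inputs from SAP 7.2: 17.8% versus 2.7%, two-sided 0.05, 84% power, 136 patients unclustered.

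- The pooled two-proportion formula gives 69 per arm (138) and the unpooled formula 67 per arm (134). Power at 68 per arm is 83.5%. The stated 136 is reproduced to within 2 patients.
- Fixed clusters: 1 + (6 − 1) × 0.01 = 1.05, and 136 × 1.05 = 142.8.
- Variable clusters: 1 + [(1.08² + 1) × 2.9 − 1] × 0.01 = 1.053 (stated 1.06). The plan's 136 × 1.06 = 144.16 is taken as 145.
- Dropout: 145 / 0.98 = 148.

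No sample-size figure is shown wrong by this point.

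**Weight of one patient.** Expected events: 72 × 0.178 = 12.8 after PFDD and 72 × 0.027 = 1.9 after PFD. One patient is 1/72 = 1.4 percentage points. One uncounted PFD event is about half of that arm's expected total (1/1.9).

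**Illustration, by assumption only.** The documents give no rate for the events at issue. Take an effective n of 72/1.06 = 67.9 per arm and power = Φ{[Δ − 1.96 √(2p̄(1 − p̄)/n)] / √[(p₁q₁ + p₂q₂)/n]}. With Δ = 0.151 and p̄ = 0.1025 this is Φ[(0.151 − 0.102)/0.0504] = 83.4%.

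| Share of events captured | Both arms affected | PFDD only affected |
|---|---|---|
| 95% | 81.2% | 80.2% |
| 90% | 78.8% | 76.6% |
| 80% | 73.3% | 67.9% |
| 70% | 66.9% | 57.6% |

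The direction is not fixed. If the planning rates already exclude these harms, counting them could also cost power: adding 1, 2, 3 or 5 points to both arms gives 80.2%, 77.2%, 74.3% or 69.1%.

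**The case against.** The strongest reply is that the written endpoint is largely right and only the field map needs checking. SAP 7.5.1 does define infection to include antibiotic-only cases. Reading WR as wound revision is an inference, and the double listing proves little alone, because the chemical-meningitis field is also listed under both headings. The missing infection row could be an extraction fault. This stands as a caution, and so the claim is that such infections may be missed. A reader might infer that they certainly score no; without the case report form, the documents do not establish that.

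A reader might also infer that culture-positive meningitis is scored no. It has a field and a row in SAP 1.1, is named under an intervention in SAP 7.5.1, and could meet the infection definition. What stands is that the lists disagree.

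The intra-operative heading can be read as injury caused at operation, since new weakness is ordinarily found afterwards and return to surgery for haemorrhage is by its wording post-operative. The protocol and the SAP also agree on that heading. This reduces the point to an ambiguity, clearest for later death, and means that resolving it touches the protocol's own wording.

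Blinded adjudication (SAP 7.4) could correct miscoding and is said to determine final outcomes. But SAP 7.5 runs the initial analysis before adjudication and places post-adjudication results among the sensitivity analyses. The rows for other complications in SAP 1.1 do not help either, because they are not in the 7.5.1 composite.

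**Conclusion.** The point holds as a mismatch of definitions on the primary endpoint, and its parts differ in certainty. The loss of ptosis and cerebellopexy from the SAP composite is plain on the page. The disagreement over true meningitis is equally plain, but whether any case would be lost depends on which list is programmed. The infection gap is a well-supported inference that the form can settle. The post-operative status of death, stroke or dissection and neurological deficit is unclear rather than excluded.

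The size is 1.4 points per misclassified patient against about 13 and 2 expected events, assuming the planning rates and 72 per arm. The share of the 17.8% at risk cannot be computed, because the row labels of Protocol Table 3 are not legible in the text available. The power figures above rest on assumed capture rates and are not estimates. A reader might go further and infer that the arms could be put in the wrong order. That would need a net excess of about 11 uncounted PFD harms (12.8 − 1.9 = 10.9), and nothing in the documents suggests it. The mismatch should still be resolved before the primary analysis is relied on, because the SAP as written yields an endpoint that differs from the protocol's.

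**What to change.** Write one component list, with a window and a named variable for each item. Use it in Protocol 10.3.3 and SAP 1.1, 5.2 and 7.5.1, and derive the primary variable from it.

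1. Restore cerebellar ptosis and cerebellopexy to SAP 7.5.1, and name a variable for each.
2. List true (bacterial) meningitis as a complication in both composites, and use one term for it throughout.
3. Code infection from any recorded infection that meets the SAP 5.2 definition ("elevated laboratory parameters in association with antibiotic treatment ± surgical debridement"). Check Form 16416 first, then keep ChiariPOWRInfection only as the wound-revision flag.
4. State that the items now headed intra-operative include those injuries, and death, when they present after surgery within the endpoint window. This touches the protocol's own wording, so record it as a dated clarification in both documents, preferably agreed without sight of results by arm. If preferred, report the primary result with and without it.

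The cost is one variable to re-derive, a few more events to adjudicate, and the wording changes. No new data collection should be needed: Protocol 7.2 and 7.4 already require complications and adverse events to be recorded through follow-up, and the adverse-event procedures under 7.2 ask for date of first occurrence and treatment.

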1.2 Secondary Objectives

Specific Aim 2: Determine if PFD provides non-inferior clinical improvement and syrinx regression compared to PFDD.

Hypothesis: Clinical improvement and syrinx regression provided by PFD will be non-inferior compared to those provided by PFDD.

Anticipated Outcome: Clinical symptoms, neurological function, and syrinx regression ≤ 12 months will be non-inferior following PFD when compared with PFDD.

- Rates of revision decompression surgery (PFD or PFDD) and progression of spinal deformity ≤12 months after PFD also will be non-inferior to PFDD. Please note that the time window is ≤12 months. When there are multiple visits within this window, the visit with the closest to 12 months after surgery will be used.
- For this aim, clinical symptoms and syrinx regression ≤12 months will be used as the primary outcome variable. Results based on the rates of revision decompression surgery and progression of spinal deformity will be exploratory.

Corresponding Variable Names for 'Clinical Improvement'

• Outcome – Scores, Limonadi/Binary -> compare for symptoms and neurological deficits

- Timeframe compare preoperative to:
- ≤ 6 weeks
- 3-6 months
- 12 (+/- 2) months (primary)
- Binary Scoring is primary
- Limonadi Scoring specifics:
- Each subject was given a score for each symptom at each visit, 2=resolved, 1=improved, 0=stable, -1 = worse.
- Symptom scores within a patient were then averaged across visits (per Limonadi paper) to get patient-level symptom-specific scores.
- These patient-level symptom-specific scores were then averaged to get a single overall score per patient.
- These single overall scores per patient were then averaged within site randomization to get group comparisons between sites randomized to PFD and sites randomized to PFDD.
- Binary Scoring specifics:
- Each subject was given a binary score for each symptom at each visit, 1=positive outcome, 0=negative outcome.
- Symptom scores within a patient were then averaged across visits (per Limonadi paper) to get patient-level symptom-specific scores.
- These patient-level symptom-specific scores were then averaged to get a single overall score per patient.
- These single overall scores per patient were then averaged within site randomization to get group comparisons between sites randomized to PFD and sites randomized to PFDD.

Symptoms						
	Double Vision					
	Sensory Symptoms					
	Weakness Symptoms					
	Dysphagia					
	Hoarseness					
	Choking					
	Sleep Apnea					
	Sheep Aphea Shortness of Breath Neck Pain Back Pain Trunk Pain Upper Extremity Pain Lower Extremity Pain Tremors Gait Ataxia Incontinence Sexual Dysfunction Headaches Papilledema* Nystagmus Disconjugate Gaze Extraocular Palsies					
	Neck Pain					
	Back Pain					
	Trunk Pain					
	Upper Extremity Pain					
	Lower Extremity Pain					
	Tremors					
	Gait Ataxia					
	Incontinence					
	Sexual Dysfunction					
	Headaches					
Neurological Deficits						
	Papilledema*					
	Nystagmus					
	Disconjugate Gaze					
	Extraocular Palsies					
	Facial Weakness					
	Disturbance in Facial Sensation*					
	Hearing Loss*					
	Hearing Loss* Hoarseness*					
	Tongue Deviation*					
	Weak Shrug*					
	Weak Neck Rotation*					
	Strength Assessment					
	Strength Status – Left Upper					
	Strength Status – Kight Opper					
	Strength Status – Left Lower					
	Light Touch Aggagment*					
	Light Touch Entire Pody*					
	Light Touch _ Torso*					
	Light Touch – Torso*					
	Light Touch Extremities Assessment*					
	LT Extremities – Left Unner*					
	LI Extremities – Lett Upper*					
	LT Extremities – Left Lower*					
	LT Extremities – Right Lower*					
	LT Extremities – Right Lower*					

Pinprick/Temp Assessment*			
Deficit Pin/Temp – Left Upper*			
Deficit Pin/Temp – Right Upper*			
Deficit Pin/Temp – Left Lower*			
Deficit Pin/Temp – Right Lower*			
Joint Pos. Sense Assessment*			
Deficit Joint Pos. Sense – Left Upper			
Extremity*			
Deficit Joint Pos. Sense – Right Upper			
Extremity*			
Deficit Joint Pos. Sense – Left Lower			
Extremity*			
Deficit Joint Pos. Sense – Right Lower			
Extremity*			
Deep Tendon Reflexes*			
Ankle Clonus*			
Babinski Reflex*			
Hoffman's Reflex*			
Gait Instability			
Romberg Response*			
Dysmetria*			

Corresponding Variable Names for 'Syrinx Regression'

- Syringomelia Present (yes/no): Follow-up Packet Section 25.0, Syringomelia
 - Syrinx Maximum AP Diameter (in mm): SyrinxMaxAPDiameter

Corresponding Variable Names for 'Progression of Spinal Deformity'

• Follow-Up Packet section 25.0 Follow-Up Radiographic Examinations, Scoliosis

Specific Aim 3: Determine if PFD is associated with superior QOL compared with PFDD. **Hypothesis:** With fewer surgical complications, PFD will be associated with superior QOL compared with PFDD.

Anticipated Outcome: PFD will have superior QOL and will show improvements in overall QOL over time (≤ 12 months post-operatively) compared to PFDD. In particular, both physical metrics (evaluated by pain frequency, pain severity and non-pain symptoms) and psychosocial metrics will improve at a higher rate and in a shorter period of time after PFD compared to PFDD. QOL will be assessed at the same time points using the Chiari Health Index Pediatrics (CHIP), and the Health Utilities-3 (HUI-3). For this aim, CHIP QOL (≤ 12 months post-operatively) will be used as the primary outcome, and HUI-3 and the domain sub-scores presented below will be assessed as the secondary outcomes. Additional, sensitivity analyses will be performed for the CHIP QOL based on the last reported CHIP QOL scores including up to 24 months post-operatively.

Corresponding Metrics for QOL:

Assumptions on dates and times were based on the following:

- Assuming 1 Month = 30 days
- From protocol, we wish to report CHIP assessments are at baseline, within 6 weeks of surgery, within 3-6 months of surgery and within 12 +/- 2 months of surgery.
- CHIP QOL was calculated via the method described in: https://thejns.org/pediatrics/view/journals/j-neurosurg-pediatr/17/1/article-p76.xml
- Only patients with complete entries were considered in the report.
- Domain sub-scores (sums of indicators) for each of the following domains of CHIP:
 - Pain Frequency
 - o Pain Severity
 - Non-Pain Symptoms
 - Psychosocial/Cognitive
- Overall QoL outcome (non-uniform weighted avg.) of the above 4 domains

2. STUDY DESIGN

This will be a cluster randomized control trial of 148 patients recruited from the 36 centers of the Park-Reeves Syringomyelia Research Consortium (PRSRC) as well as an additional 7 research centers. Randomization will occur at the center level with standardized surgical technique, and data will be recorded in the PRSRC prospective registry. In order to examine the main comparative effectiveness research (CER) question of surgical complications and potential harm to patients

(Aim 1), intra-operative complications and short (≤ 6 months) and long-term (6-12 months) postoperative complications will be recorded for both PFD and PFDD. For Aim 2, clinical symptoms, neurological function, and modified Chicago Chiari Outcome Scale (mCCOS) [22] scores will be measured pre-operatively and longitudinally at ≤ 6 weeks, 3-6 months, and 12 ± 2 months after surgery. MRIs will be obtained (at a minimum) ≤ 6 months pre-operatively and 12 ± 2 months post-operatively to compare the effect of surgery on syrinx size and spinal deformity. In order to test Aim 3 hypothesis, QOL will be assessed at the same time points using the Chiari Health Index Pediatrics (CHIP), and the Health Utilities-3 (HUI-3), holistically evaluating patients across psychosocial and physical dimensions.

3. SELECTION AND ENROLLMENT OF PARTICIPANTS.

